#### Control Group Definition

The control group will include patients who, during hospitalization at the Old Civil Hospital of Guadalajara “Fray Antonio Alcalde”, were identified by the Nephrology Service as having severe acute kidney injury that had resolved or was in the process of recovery. These patients will have been discharged with standard post-AKI management and care, without the addition of antibiotic prophylaxis.

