### Materials and Methods

- This study will be a phase 2, randomized, prospective, double-blind, investigator-initiated, parallel-group, placebo-controlled clinical trial conducted at the Hospital Civil de Guadalajara “Fray Antonio Alcalde”, Guadalajara, Mexico. All patients with AKI receiving nephrology consultation will be considered for inclusion.
- The diagnosis of AKI will follow the Kidney Disease: Improving Global Outcomes (KDIGO) serum creatinine criteria. In accordance with the recommendations of the 31st Acute Disease Quality Initiative Group regarding the design of clinical trials for AKI treatments, the subphenotype of patients at the highest risk of post-AKI infections will be selected. This study will be considered a phase 2 randomized, double-blind, placebo-controlled trial meeting efficacy (AKI trajectory and eGFR evaluation), feasibility (patient recruitment and protocol adherence), and safety (adverse events and drug reactions) objectives.
- Group randomization will be performed using the clinical trial randomization tool available at <http://www.winepi.net/f108.php>, employing traditional block randomization. Sequences for each arm and stratum will be generated using maximal asymptotic randomization.
- Patients will be recruited on an outpatient basis to document any infectious event of any kind occurring within the first 90 days, as well as cases of rehospitalization due to infection within the same period at the Hospital Civil de Guadalajara “Fray Antonio Alcalde”.

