#### Sampling Method

Potential participants for this study will be identified during routine hospital rounds for patients with acute kidney injury (AKI) and through concurrent review of medical records to confirm eligibility. If a patient is deemed eligible, the principal investigator will contact them to explain the study and provide a participant information and consent form.

After discussion with the patient and family members, the nephrology staff will obtain written informed consent prior to any study-related evaluations.

The intervention drug will be trimethoprim–sulfamethoxazole 800/160 mg, administered under double-blind conditions. Blinding will be achieved by ensuring that participants do not witness preparation of the study medication, and by assigning unblinded study personnel—who will not participate in outcome assessments—to handle preparation and administration.

The placebo will consist of magnesium tablets, administered at the same frequency—one tablet every 48 hours for three months.

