#### Inclusion Criteria

Patients with severe AKI and known baseline serum creatinine (SCr) levels—defined as the most recent SCr value within the six months preceding hospitalization—will be included. Participants must also have available serum creatinine data for the months following discharge to assess major adverse kidney events (MAKE) at 90 days post-AKI.

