## Operationalization of Variables

### Independent Variable:

- Treatment: Administration of the study drug versus placebo (categorical variable with two levels: active treatment or placebo).

Dependent Variables (Primary Outcomes):

- Development of gastrointestinal infections — categorical nominal binary variable (yes/no)
- Development of upper respiratory infections — categorical nominal binary variable (yes/no)
- Development of lower respiratory infections — categorical nominal binary variable (yes/no)
- Development of urinary tract infections — categorical nominal binary variable (yes/no)
- Development of soft tissue infections — categorical nominal binary variable (yes/no)
- Rehospitalization due to infection — categorical nominal binary variable (yes/no)
- Development of septic shock — categorical nominal binary variable (yes/no)
- Requirement for long-term renal replacement therapy — categorical nominal binary variable (yes/no)
- Death from any cause — categorical nominal binary variable (yes/no)
- Progression to chronic kidney disease or  $\geq 50\%$  decline in eGFR — categorical nominal binary variable (yes/no)
- Worsening renal function with  $\geq 25\%$  decline in eGFR due to infection — categorical nominal binary variable (yes/no)
- Presence of hyperkalemia — categorical nominal binary variable (yes/no)
- Adverse drug reactions — categorical nominal variable

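### The control group has its own definition, with a recovery condition found in no common eligibility text and no mention of allocation or placebo, which does not fit the randomised placebo design

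*Protocol*

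**What the plan says.** Materials and Methods describes a "randomized, prospective, double-blind, investigator-initiated, parallel-group, placebo-controlled clinical trial" with block randomisation. Sampling Method gives one route into the study for everyone: identification on hospital rounds, a check of eligibility, then consent. It also names the comparator: "The placebo will consist of magnesium tablets, administered at the same frequency". Operationalization of Variables codes treatment with two levels, active or placebo: "Administration of the study drug versus placebo".

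The section that follows Sampling Method, Control Group Definition, describes controls on their own terms. They are inpatients whom the Nephrology Service identified as having "severe acute kidney injury that had resolved or was in the process of recovery". It continues: "These patients will have been discharged with standard post-AKI management and care, without the addition of antibiotic prophylaxis".

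The eligibility text for the trial as a whole contains no such recovery condition. Inclusion Criteria opens with "Patients with severe AKI and known baseline serum creatinine (SCr) levels" and goes on to creatinine availability. Study Population requires severe AKI, discharge and nephrology follow-up. Exclusion Criteria covers recent AKI, age, stage 5 CKD, dialysis or transplant, short stay and incomplete data.

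**The concern.** In a parallel-group randomised trial both arms come from one eligible population and differ only by allocation. A separate description of who the controls are has no place in that design, and this one differs from the common criteria in two ways.

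- **Who they are.** A recovery condition is attached to controls and to nobody else.
- **What they receive.** Controls are described by standard care without prophylaxis, with no mention of a placebo tablet or of being allocated.

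Staff who worked from this section alone could hold controls to a condition that active-arm patients need not meet, or could treat untreated standard-care patients as the comparator. The first would put a difference in kidney recovery between the arms. The protocol itself regards the course of kidney function after AKI as relevant to infection: Background and Theoretical and Conceptual Framework link transition to CKD and eGFR decline with infection risk. The second would remove the placebo and, with it, the participants' blinding. The comparisons named in Statistical Analysis (chi-square or Fisher's exact test, Mann–Whitney, log-rank) are unadjusted, so they would not correct an imbalance in recovery status.

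**Working it through.** The point itself contains no figure to recompute, so the check is to set the sections side by side.

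| Feature | Design and eligibility sections | Control Group Definition |
|---|---|---|
| Allocation | Block randomisation (Materials and Methods) | Not mentioned |
| Comparator | Magnesium tablets on the same schedule as the drug (Sampling Method); placebo level of the treatment variable (Operationalization of Variables) | Standard care without prophylaxis; placebo not mentioned |
| Recovery of AKI | No condition (Study Population, Inclusion Criteria, Exclusion Criteria) | Resolved or recovering |
| Definition of the active arm's patients | Common criteria only; no separate definition | Not applicable |

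**Step 1: what controls receive.** The absence of prophylaxis is true both of a patient on placebo plus standard care and of a patient on standard care alone. Taken with Sampling Method and Operationalization of Variables, the first meaning is available and is the natural one. On this feature the section is incomplete and does not conflict outright.

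**Step 2: who controls are.** Reading control as placebo plus standard care does not resolve the recovery condition. A patient with severe AKI that is not recovering can satisfy the common criteria but cannot satisfy the control definition. There are two possibilities. If recovery is meant for all patients, the common criteria omit it. If it is not, the control definition is wrong to include it. The protocol needs correction in either case.

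**Step 3: is the wording isolated?** Elimination Criteria refers to stopping, or changing the dose of, the prophylactic antibiotic and does not mention placebo tablets. Required Resources lists trimethoprim–sulfamethoxazole tablets and no placebo supply. Neither shows that an untreated comparator is planned, but both leave the control arm's treatment less clear than it should be.

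**Step 4: effect on the sample size.** Sample Size gives 60 per group for 59% against 29.5% at 90% power. With pooled variance, mean proportion (0.59 + 0.295)/2 = 0.4425 and two-sided 0.05, n = 2 × 0.4425 × 0.5575 × (1.960 + 1.282)² / 0.295² ≈ 59.6, which rounds up to 60. None of these inputs involves the control definition, so correcting the wording leaves this calculation unchanged.

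**The case against.** The strongest reply is that the design is stated clearly elsewhere. Randomisation, blinding and placebo appear in Justification and in Materials and Methods, and the placebo is specified just before the control definition. The inclusion and exclusion criteria are not arm-specific, and there is one recruitment route. Under concealed random allocation a condition for one arm could not be applied without abandoning the stated design. Problem Definition also describes the whole target population as recovering from severe AKI, so the recovery phrase may simply describe everyone.

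Most of this stands, and it limits what can be concluded. A reader might infer that controls are an untreated, non-randomised cohort, or that the two arms will in fact be recruited under different rules. The protocol does not support either inference: the section is silent on placebo and allocation and does not exclude them, and the other sections state both.

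A reader might also try to size the bias from the hazard ratio of 1.55 for AKI-to-CKD transition in Background. If a fraction f of the active arm and none of the controls carried that risk, the average hazard would rise by f × 0.55, that is 5.5% at f = 10% and 22% at f = 40%. These figures should not be used, for four reasons:

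- Nothing in the protocol anchors f.
- The hazard ratio is univariate and concerns transition to CKD, not non-recovery at discharge.
- Infection surveillance in that cohort began three months after AKI, whereas this trial observes the first 90 days after discharge.
- Controls still recovering may later progress to CKD, so zero in that arm does not follow.

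The direction is not settled either. The same Background reports similar post-AKI eGFR in patients with and without infection (P = 0.215). The cohort with a 4.5-fold increase within 30 days, cited in Theoretical and Conceptual Framework, is reported without a stated comparator, so it does not contrast recovering with non-recovering patients.

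The reply does not remove the recovery condition from the control definition or add it to the common criteria. A phrase in the rationale is not an eligibility rule.

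**Conclusion.** The Control Group Definition is wrong as written. It is inconsistent with the rest of the protocol, by omission on allocation and placebo and by addition on recovery status. Applied literally, it would set an entry condition for one arm only or allow a standard-care comparator, and so put the comparability of the arms at risk. That risk depends on someone following the section in place of the design sections; it is not an established feature of how the trial will run. No size or direction of bias can be derived from the document. The point does not depend on a statistical analysis plan, because eligibility and the definition of control belong in the protocol. It should be corrected because the conflict concerns who enters each arm and the remedy is simple.

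**What to change.** 1. Delete the separate control definition. State instead that both arms are randomised from the same patients, namely those who meet the Inclusion and Exclusion Criteria, and that control means placebo plus standard post-AKI care.
2. The sponsor should reconcile whether recovery status is an entry condition. If it is, place it in the common criteria, in a form that can be verified and assessed before randomisation for both arms. If it is not, drop it.
3. Align Elimination Criteria and Required Resources so that they refer to study medication in both arms, including the placebo.

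The cost is protocol wording only. The stated sample size calculation does not change. If recovery becomes a common criterion it could narrow the pool of recruitable patients; the protocol gives no figure from which to judge by how much.

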#### Inclusion Criteria

Patients with severe AKI and known baseline serum creatinine (SCr) levels—defined as the most recent SCr value within the six months preceding hospitalization—will be included. Participants must also have available serum creatinine data for the months following discharge to assess major adverse kidney events (MAKE) at 90 days post-AKI.

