### Research Question:

Does administration of trimethoprim-sulfamethoxazole 800/160 mg every 48 hours for 90 days reduce the risk of infections in patients who have experienced severe acute kidney injury after hospital discharge?

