### Observation Unit

Patients diagnosed with severe AKI will be monitored for a period of 90 days after hospital discharge. Each participant will be evaluated based on infection incidence, rehospitalization, adverse events, and other health outcomes related to trimethoprim–sulfamethoxazole administration. Observation will focus on collecting clinical data and health outcomes specific to each participant.

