#### Exclusion Criteria

Patients will be excluded if they: Experienced AKI within the previous three months, Are younger than 18 years, Have CKD stage 5, chronic dialysis, or kidney transplant, Had a hospital stay shorter than 48 hours, Have incomplete data preventing full análisis

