#### Statistical Analysis

An intention-to-treat approach will be adopted, including all randomized participants who receive the intervention, for both primary and secondary outcomes.

Categorical variables will be expressed as counts and percentages (%) and compared using either the chi-square test or Fisher’s exact test, as appropriate.

Continuous variables will be reported as median values (IQR), since normal distribution is not expected according to the Shapiro–Wilk test; between-group comparisons will be performed using the Mann–Whitney U test.

A repeated-measures analysis of variance (ANOVA) will be used to compare variables over time between groups. A Kaplan–Meier survival curve will be plotted for both groups and compared using the log-rank test. Missing data will be imputed using the mean linear interpolation method.

All statistical tests will be two-tailed, and a p-value < 0.05 will be considered statistically significant.

The analyses and figures will be performed using MedCalc software (Version 22.0.21, Ostend, Belgium) and GraphPad Prism (Version 10.2.3, Boston, Massachusetts, USA).

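### An inclusion criterion requires post-discharge creatinine that can exist in full only after randomisation, so applying it removes randomised patients on follow-up and contradicts the intention-to-treat rule

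*Protocol*

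**What the plan says.** - **Inclusion Criteria:** "Participants must also have available serum creatinine data for the months following discharge to assess major adverse kidney events (MAKE) at 90 days post-AKI". This is worded as a mandatory condition of entry.
- **Exclusion Criteria:** patients are also left out if they "Have incomplete data preventing full análisis". No time point is given.
- **Sampling Method:** candidates are found on hospital rounds and "through concurrent review of medical records to confirm eligibility", before the patient is approached for consent.
- **Materials and Methods:** "Patients will be recruited on an outpatient basis", so that events in the first 90 days can be documented.
- **Research Question:** the question is whether the study drug given "for 90 days reduce the risk of infections in patients who have experienced severe acute kidney injury after hospital discharge".
- **Observation Unit:** "Patients diagnosed with severe AKI will be monitored for a period of 90 days after hospital discharge".
- **Statistical Analysis:** "An intention-to-treat approach will be adopted, including all randomized participants who receive the intervention", for primary and secondary outcomes alike. The same section adds: "Missing data will be imputed using the mean linear interpolation method".
- **Operationalization of Variables:** all-cause death and long-term renal replacement therapy (RRT) are listed as yes/no outcomes.
- **Elimination Criteria:** a further list removes patients after enrolment for stopping the prophylaxis, for taking a different dose, or for non-infectious readmission.

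**The concern.** An eligibility criterion should be decidable from what is known before randomisation. This one depends on data that the trial itself will generate. If it is enforced, whether a patient counts as included depends on what happened after allocation: survival, attendance and contact with the hospital. Each of these can be related to infection and to treatment.

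Patients without a qualifying creatinine would take their deaths and infections out of the data with them. If such losses differ by arm, the groups compared are no longer those that were randomised, and the primary infection comparison suffers as well as the kidney endpoint. The protocol also tells the analyst to do the opposite in its Statistical Analysis section, so two analysts following it in good faith could analyse different sets of patients.

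**Working it through.** **Timing.** The required data cover the months after discharge and must support a 90-day assessment.

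- Under Sampling Method, eligibility is confirmed from concurrent records of patients found on hospital rounds. No post-discharge value exists yet.
- Under Materials and Methods, recruitment is outpatient. One early post-discharge value might then precede randomisation, but the data for a 90-day assessment cannot.

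On either account the criterion can be fully checked only during or after follow-up.

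**Conflict.** Take a patient who is randomised and treated, and then dies or is lost with no qualifying creatinine. Under Statistical Analysis the patient stays in. Under Inclusion Criteria the patient was never eligible. Limiting intention-to-treat to those who receive the intervention does not help, because this patient received it. The undated incomplete-data exclusion may refer to baseline records, but as worded it permits the same removal.

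**The plan's own figure.** Inputs from Sample Size: p1 = 0.59, p2 = 0.295, 95% confidence, 90% power, 60 per group. Two-sided testing comes from Statistical Analysis.

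- Mean proportion: p̄ = (0.59 + 0.295)/2 = 0.4425, so 2p̄(1−p̄) = 0.4934.
- Separate variances: 0.59×0.41 + 0.295×0.705 = 0.4499.
- With the pooled variance in both terms: n = 0.4934 × (1.96 + 1.2816)² / 0.295² = 59.6, rounded up to 60. The stated figure reproduces.
- With the pooled variance under the null only, n = 58.

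**Power if removal is equal by arm and unrelated to infection.** Power = Φ[(0.295√n − 1.96√0.4934)/√0.4499].

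| Removed per arm (assumed) | n per arm | Power |
|---|---|---|
| 0 | 60 | 91.2% |
| 3 (5%) | 57 | 89.8% |
| 6 (10%) | 54 | 88.1% |
| 9 (15%) | 51 | 86.2% |

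**Bias if removal is related to infection and confined to one arm.** The protocol gives no loss rate, so the fraction removed, d, is assumed. If all those removed are infected, the observed risk is (p − d)/(1 − d). For example, (0.59 − 0.05)/0.95 = 0.568.

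| d | Control 59% becomes | Difference from 29.5% (points) | Active 29.5% becomes | Difference from 59% (points) | 30% in both arms: affected arm becomes | Spurious difference (points) |
|---|---|---|---|---|---|---|
| 3/60 | 56.8% | 27.3 | 25.8% | 33.2 | 26.3% | 3.7 |
| 6/60 | 54.4% | 24.9 | 21.7% | 37.3 | 22.2% | 7.8 |
| 9/60 | 51.8% | 22.3 | 17.1% | 41.9 | 17.6% | 12.4 |

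The planned difference is 29.5 points. The 30% risk is the other infection rate given in Sample Size. With 30% in both arms, equal removal from both creates no difference.

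**A less extreme pattern, also assumed.** True risk is 30% in both arms. One arm loses 30% of its infected and 10% of its uninfected patients; the other loses 10% of each. The first arm shows 0.30×0.70/(0.30×0.70 + 0.70×0.90) = 0.21/0.84 = 25.0%, and the other stays at 30.0%. That is a spurious 5-point difference.

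**The case against.** The strongest reply is that the sentence governs entry only. The protocol has its own list for removal after enrolment, missing creatinine is not on it, and the sponsor may have meant patients in whom follow-up creatinine can be expected. That may well be the intent. But the text demands that the data be available, and the undated incomplete-data exclusion points the same way. A rule that cannot be checked at entry either has no effect or takes effect later.

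The protocol does not define which value qualifies. If a day-90 value is needed, everyone who dies earlier fails. If an earlier value is enough, a patient who dies or is readmitted after it could still qualify, and the problem shrinks. This stands as an uncertainty about who would be removed. It does not rescue the wording, which asks for data over months and sufficient for a 90-day assessment.

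Interpolation fills gaps between observed values, so it can coexist with a demand for some creatinine. That is fair, and the intention-to-treat conflict carries more weight than the imputation conflict. The imputation rule still shows that the plan expects analysed patients to have missing data.

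The one-arm, all-infected removals are extreme, and the trial is double-blind. Patients readmitted to the study hospital with infection may be more likely to have creatinine recorded. This stands: the figures are illustrations, not forecasts.

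The Elimination Criteria conflict with intention-to-treat in their own right. That is a related problem, and the present point does not depend on it.

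**Conclusion.** The concern holds. As written, the criterion cannot be fully met at enrolment, and enforcing it means excluding randomised patients on follow-up data, against the protocol's own analysis rule. Together with the undated incomplete-data exclusion and the Elimination Criteria, the protocol does not define a single analysis set for its primary comparison.

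The size and direction of any bias cannot be derived from the protocol, which gives no loss rate. The consequence ranges from a modest loss of power, when removal is equal by arm and unrelated to infection, to a spurious difference or a distorted effect, when it is related to infection and differs by arm. This conclusion rests on the literal text and the timing; the removal figures only show scale.

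**What to change.** 1. **Inclusion Criteria:** delete the sentence on post-discharge creatinine. Creatinine at 90 days becomes a follow-up assessment.
2. **Exclusion Criteria:** limit the incomplete-data clause to baseline data needed to confirm eligibility that are missing before randomisation.
3. **Statistical Analysis:** keep all randomised patients in the primary analysis.
4. **Elimination Criteria:** reconcile with item 3. For the analysis set, these events should not remove anyone from the primary analysis and could at most define a secondary per-protocol set.
5. **Endpoint handling:** count death and long-term RRT as events where they are part of the endpoint, whether or not a 90-day creatinine exists. Treat a missing 90-day creatinine in survivors as missing outcome data, with a sensitivity analysis.

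The cost is protocol wording, with no extra patients or visits. The downside is that some missing 90-day creatinine values must be handled in the analysis.

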#### Secondary Objectives:

To evaluate the risk of rehospitalization, infection-related rehospitalization, septic shock, major adverse kidney events (MAKE) at 90 days, incidence of hyperkalemia, and new episodes of acute kidney injury. Adverse events (AEs) will be coded using the Medical Dictionary for Regulatory Activities (MedDRA) and classified as mild, moderate, or severe. AEs of special interest include skin rash, erythema, nausea, vomiting, headache, and tachycardia.

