### Working Hypothesis

Hypothesis: Administration of trimethoprim–sulfamethoxazole 800/160 mg every 48 hours for 90 days reduces the risk of infections.

Null Hypothesis: Administration of trimethoprim–sulfamethoxazole 800/160 mg every 48 hours for 90 days does not reduce the risk of infections.

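### The creatinine behind MAKE and the eGFR outcomes is drawn while patients are still on trimethoprim, which biases those components against the active arm by an unknown amount

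*Protocol*

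**What the plan says.** The Working Hypothesis is that trimethoprim-sulfamethoxazole "800/160 mg every 48 hours for 90 days reduces the risk of infections", and the Research Question places the course after hospital discharge. Sampling Method defines the comparator: "The placebo will consist of magnesium tablets, administered at the same frequency".

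The kidney outcomes appear in several places:

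- Inclusion Criteria requires "serum creatinine data for the months following discharge to assess major adverse kidney events (MAKE) at 90 days post-AKI".
- Secondary Objectives lists "major adverse kidney events (MAKE) at 90 days, incidence of hyperkalemia, and new episodes of acute kidney injury".
- Materials and Methods states: "The diagnosis of AKI will follow the Kidney Disease: Improving Global Outcomes (KDIGO) serum creatinine criteria". The same section names AKI trajectory and eGFR as what efficacy will be judged on.
- Operationalization of Variables lists CKD progression or an eGFR decline of at least 50%, and an eGFR decline of at least 25% attributed to infection. It also lists long-term renal replacement therapy and death.

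Exclusion Criteria removes anyone who "Had a hospital stay shorter than 48 hours". Elimination Criteria removes patients who stop the prophylactic antibiotic before three months. Serum creatinine is the only filtration marker named for these outcomes. The protocol provides no creatinine after treatment ends and no rule for drug-related creatinine rises.

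**The concern.** Trimethoprim reversibly blocks tubular secretion of creatinine, so measured creatinine can rise and calculated eGFR fall while filtration is unchanged. This is general pharmacology, not something the protocol states, and its size on this schedule is unknown. Only one arm receives trimethoprim. Randomisation and blinding do not remove a measurement shift of this kind, because the treatment itself causes it.

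If the deciding creatinine is drawn on treatment, part of any difference in CKD progression, eGFR decline or new AKI may be measurement and not injury. It could look like kidney harm, or it could hide a kidney benefit from fewer infections. An analysis plan cannot recover an off-treatment sample that was never taken.

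**Working it through.** **The plan's own figure.** No figure is given for any kidney outcome. The only design calculation that can be reproduced is for infection: 59% against 29.5%, two-sided 5%, 90% power. With the mean proportion 0.4425, n = 2 × 0.4425 × 0.5575 × (1.96 + 1.2816)² / 0.295² = 59.6, so 60 per group as stated. It does not depend on creatinine.

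**Timing.** Let g be the days from AKI to discharge and s the days from discharge to the first tablet, neither negative.

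- Day 90 post-AKI is day 90 - g after discharge.
- The 90-day course ends on day 90 + s after discharge.
- The MAKE creatinine therefore falls g + s days before the course ends.

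If AKI was present at admission, the minimum 48-hour stay makes g at least 2, so the sample falls on day 88 after discharge or earlier. If AKI developed later in the stay, g may be smaller but is still not negative. If the 90 days were counted from discharge instead, as for infection, the sample would still fall no later than the end of dosing. The only baseline creatinine the protocol defines is a pre-hospital value, so a shift on study drug would not cancel in a change from that baseline.

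**Size of the apparent eGFR fall.** Assumptions, none from the documents: creatinine is multiplied by r with filtration unchanged, and eGFR is proportional to creatinine^-e. The protocol names no eGFR equation, so e = 1.2 is used, with e = 1.0 as a check. Apparent fall = 1 - r^-e.

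| Creatinine rise | e = 1.2 | e = 1.0 |
|---|---|---|
| 10% | 10.8% | 9.1% |
| 20% | 19.7% | 16.7% |
| 30% | 27.0% | 23.1% |

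**Thresholds reached by the shift alone.** The rise needed for a decline d is (1 - d)^(-1/e) - 1.

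- 25% decline: 27% (e = 1.2) to 33% (e = 1.0).
- 50% decline: 78% (e = 1.2) to 100% (e = 1.0).

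**CKD classification.** For any eGFR cut-off C, a patient whose true eGFR lies between C and C × r^1.2 is reported below C. The factor r^1.2 is 1.12, 1.24 and 1.37 for rises of 10, 20 and 30%. Patients up to 12, 24 or 37% above the cut-off could therefore be reclassified.

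**50% decline with ordinary variation added.** With no true change and an assumed SD of 0.20 for the change in log eGFR, the share crossing is Φ((ln 0.5 + 1.2 ln r)/0.20). This gives 0.03% on placebo and 0.2, 0.9 and 2.9% on active drug, under two patients in 60 (60 × 0.029 = 1.7). With an SD of 0.25 on log creatinine (1.2 × 0.25 = 0.30 on log eGFR) it is 1.0% against 2.7, 5.7 and 10.4%. The low exposure of this threshold therefore depends on patients being reasonably stable.

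**New AKI.** The protocol gives neither a numerical cut-off nor a time window, so no rate is calculated. The direction of bias is the same.

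**The case against.** The strongest reply is that the mechanism and every magnitude come from outside the protocol, and that nothing in it supports a 10 to 30% rise for one tablet every 48 hours. That stands. The direction follows from the design, but the size is assumed.

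A reader might infer that MAKE as a whole is invalid, or that the kidney comparisons cannot answer their objectives. The documents do not support this. Death and renal replacement therapy are not defined by creatinine, and the 50% decline is little exposed to the shift alone.

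A reader might also infer that large numbers of active patients would be counted as events. Under the same model with SD 0.20, Φ((ln 0.75 + 1.2 ln r)/0.20) gives 7.5% crossing a 25% decline on placebo and 19, 37 and 55% on active drug. These are not predicted rates for any listed outcome, because the protocol counts a 25% decline only when it is due to infection. A shift in an uninfected patient does not qualify. How attribution is decided is not stated, so the filter's strength is unknown.

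Two further limits apply. Sampling dates are inferred from the 90-day windows, not stated. The on-treatment conclusion holds for patients who complete the course. Statistical Analysis states intention to treat, and under that approach patients who stopped early would be kept and could be off drug when sampled, which would dilute the shift.

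Finally, the primary objective, hypothesis and sample size concern infection. The bias runs against the active drug, so it would not create a false claim of kidney benefit.

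**Conclusion.** The point holds for the creatinine-based components: CKD progression, eGFR decline and evaluation, and creatinine-defined new AKI. Completers are measured within the treatment window, only one arm takes trimethoprim, and no off-treatment value is planned.

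The direction is against the active arm. The size is not in the documents. Under the assumed 10 to 30% rise and exponent 1.2, the apparent eGFR fall is 11 to 27%. This is enough to matter for CKD classification and for a 25% threshold before attribution to infection, but rarely enough on its own for a 50% decline.

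This is a cheap improvement to the kidney outcomes, not a threat to the infection question. The heading in Operationalization of Variables places the eGFR outcomes among the primary ones, but the stated primary objective is infection, and Secondary Objectives lists MAKE and new AKI.

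**What to change.** In Inclusion Criteria and Operationalization of Variables, state that the creatinine used for the CKD and eGFR component of MAKE, and for eGFR decline, is drawn in both arms at one fixed time after the last study tablet, for example 7 to 14 days. Count time from discharge, as the rest of the trial does, and not from the AKI episode. If dosing starts at discharge and runs 90 days, the sample falls on days 97 to 104 (90 + 7 to 90 + 14). The interval assumes the effect has worn off by then; the sponsor should confirm this. Report on-treatment creatinine separately as safety data.

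Keep counting new AKI episodes as they occur. Do not require the rise to persist off treatment: that would discard a genuine episode in month one that had resolved by the final sample, which Secondary Objectives sets out to capture. Report new AKI with the caveat that small creatinine-only rises on treatment may not reflect lost filtration.

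The cost is protocol wording, one to two weeks more follow-up, and a kidney endpoint slightly after day 90. Treatment, the infection outcome and the sample size do not change.
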